4.2. Extent of Exposure

Extent of exposure to study drug will be examined by assessing the total duration of study drug exposure and the level of adherence to the study drug regimen specified in the protocol.

4.2.1. Duration of Exposure to Study Drug

Total duration of exposure to study drug will be defined as last dose date minus first dose date plus 1, regardless of any temporary interruptions in study drug administration, and will be expressed in weeks using up to 1 decimal place (eg, 4.5 weeks). If subjects are continuing on study drug, use the last study drug end date, clinical visit date, or laboratory visit date, whichever occurred last during the on-treatment period [or use the data cutoff date for analysis] to impute the last dose date for the calculation of the duration of study drug exposure.

The total duration of exposure to study drug will be summarized using descriptive statistics (number of subjects [n], mean, standard deviation [SD], median, first quartile [Q1], third quartile [Q3], minimum, and maximum) and using the number (ie, cumulative counts) and percentage of subjects exposed through the following time periods: Baseline (Day 1), Week 1 (Day 7); Week 4 (Day 28), Week 8 (Day 56), Week 12 (Day 84). A 3-day window is applied to the last planned on-treatment visit to match with the protocol-specified visit window. Summaries will be provided for the Safety Analysis Set.

4.2.2. Adherence to Study Drug

The total number of tablets administered will be summarized using descriptive statistics (n, mean, SD, median, Q1, Q3, minimum, and maximum).

The presumed total number of tablets administered to a subject will be determined by the data collected on the drug accountability CRF using the following formula:

$$\text{Total Number of Doses Administered} = \left(\sum \text{No. of Tablets Dispensed} \right) - \left(\sum \text{No. of Tablets not administered} \right)$$

The level of adherence to the study drug regimen will be assessed based on the total amount of study drug administered relative to the total amount of study drug prescribed at baseline.

The level of adherence will be expressed in percentage using the following formula:

$$\text{Level of Adherence(\%)} = \left(\frac{\text{Total Amount of Study Drug Administered}}{\text{Total Amount of Study Drug Prescribed at baseline}} \right) \times 100$$

Note: If calculated adherence is greater than 100%, the result will be set to 100%.

In this study, the total amount of LDV/SOF (90 mg/400 mg) prescribed for 12 weeks of treatment would require 84 tablets. For LDV/SOF (22.5 mg/ 100 mg), the total amount of tablets would be 336.

Subjects who prematurely discontinue study drug for lack of efficacy (ie, virologic failure) will have the total amount of study drug prescribed calculated up to the first date when virologic failure criteria were met. For virologic failure confirmed by 2 consecutive measurements the date of the first measurement will be used. If there are study drug bottles dispensed on or after the subject first met virologic failure criteria, these bottles will not be included in the calculation of adherence. If a bottle is dispensed and the bottle is returned empty, then the number of tablets returned will be entered as zero. If a bottle is dispensed but not returned (missing), the number of tablets taken from that bottle will be counted as zero.

Descriptive statistics for the level of adherence (n, mean, SD, median, Q1, Q3, minimum, and maximum) with the number and percentage of subjects belonging to adherence categories (eg, < 80%, ≥ 80 to < 90%, ≥ 90%) will be provided for the Safety Analysis Set. No inferential statistics will be provided.

A separate by-subject listing of study drug administration and drug accountability will be provided by subject ID number (in ascending order) and visit (in chronological order).

4.3. Protocol Deviations

A summary of important protocol deviations will be provided by the Clinical Operations group for subjects in the Safety Analysis Set.

5. BASELINE CHARACTERISTICS

5.1. Demographics

Subject demographic variables (ie, age, sex, race, and ethnicity) will be summarized using descriptive statistics (n, mean, SD, median, Q1, Q3, minimum, and maximum) for age, and using the numbers and percentages of subjects for age categories (≤ 15 years old, > 15 years old), sex, race, and ethnicity. Age is calculated in years at the date of initial study drug administration. If a subject did not receive study drug after enrollment, the subject's age will be calculated from the date that the subject signed the informed consent form. The summary of demographic data will be provided for the Safety Analysis Set.

A by-subject demographic listing will be provided by subject ID number in ascending order.

5.2. Other Baseline Characteristics

Other baseline characteristics include:

- weight in kg
- height in cm
- body mass index (BMI; in kg/m^2) as a continuous variable
- IL28B (CC, Non-CC (CT, TT))
- HCV genotype and subtypes
- cirrhosis (presence, absence, unknown)
- baseline HCV RNA (\log_{10} IU/mL) as a continuous variable and as categories $< 800,000$ IU/mL, $\geq 800,000$ IU/mL)
- baseline ALT (U/L) as a continuous variable and as categories ($\leq 1.5 \times \text{ULN}$, $> 1.5 \times \text{ULN}$)
- prior HCV treatment experience (treatment naïve or treatment experienced)
- most recent HCV treatment response (Non-Responder, Relapse/Breakthrough, other including early treatment discontinuation, met a virologic stopping rule, or unknown) for treatment-experienced subjects
- Creatinine clearance (CrCL) using the Schwartz formula as follows:

Creatinine clearance ($\text{mL}/\text{min}/1.73\text{m}^2$) = $k \times \text{height (cm)} / \text{serum creatinine (mg/dL)}$ where k , proportionality constant, is:

0.70: for adolescent males ≥ 12 years old

0.55: for adolescent females ≥ 12 years old
0.55: for children (≥ 2 and < 12 years old)

These baseline characteristics will be summarized using descriptive statistics (n, mean, SD, median, Q1, Q3, minimum, and maximum) for continuous variables and using the numbers and percentages of subjects for categorical variables. The summary of baseline characteristics will be provided for the Safety Analysis Set.

A by-subject listing of other baseline characteristics will be provided by subject ID number in ascending order.

A separate by-subject data listing for prior HCV treatment and response will be provided for all subjects. The listing will display the prior HCV treatment experience for all subjects as well as the prior HCV regimen and treatment, the treatment duration, and the prior HCV treatment response for treatment experienced subjects.

5.3. Swallowability Assessment for LDV/SOF Tablets

Swallowability Assessment (Able to swallow LDV/SOF FDC 90mg/400 mg or LDV/SOF FDC 22.5 mg/100 mg placebo tablet) will be summarized using the numbers and percentages of subjects in each swallowability category (ie, Able to Swallow, Unable to Swallow).

A by-subject listing of Swallowability of LDV/SOF FDC tablets will be provided by subject ID number in ascending order.

5.4. Medical History

General medical history (ie, conditions not specific to the disease being studied) data will be collected at screening and listed only. General medical history data will not be coded.

A by-subject listing of disease-specific medical history will be provided by subject ID number (in ascending order) and medical history of abnormalities (in chronological order).

6. EFFICACY ANALYSES

6.1. Primary Efficacy Endpoint

6.1.1. Definition of the Primary Efficacy Endpoint

The primary efficacy endpoint is SVR12 defined as HCV RNA < LLOQ (ie, < 50 IU/mL) 12 weeks after discontinuation of all study drugs in the FAS. The artus® HCV RG RT-PCR Kit by QIAGEN March 2015 are used to measure HCV RNA.

6.1.2. Primary Analysis of the Primary Efficacy Endpoint

The SVR12 rate in each of the HCV genotypes and overall will be calculated along with 2-sided 95% exact CI based on Clopper-Pearson method {20839}. No statistical hypothesis testing will be performed.

6.1.3. Subgroup Analysis of the Primary Efficacy Endpoint

Point estimates and 95% exact CIs of the SVR12 rates will be displayed for each subgroup outlined in Section 3.4.

A Forest plot will graphically present estimates and 95% CIs in SVR12 rates for each of the subgroups.

6.2. Secondary Efficacy Endpoints

6.2.1. Definition of Secondary Efficacy Endpoints

Secondary efficacy endpoints include the following:

- The proportion of subjects with HCV RNA < LLOQ at 4 and 24 weeks after discontinuation of treatment (SVR4 and SVR24)
- The proportion of subjects with HCV RNA < LLOQ while on treatment by study visit
- HCV RNA (\log_{10} IU/mL) and change from baseline in HCV RNA (\log_{10} IU/mL) through end of treatment (EOT)
- The proportion of subjects with virologic failure as the following:
 - On-treatment virologic failure
 - HCV RNA \geq LLOQ after having previously had HCV RNA < LLOQ, while on treatment, confirmed with 2 consecutive values (note, second confirmation value can be posttreatment), or last available on-treatment measurement with no subsequent follow up values (ie, breakthrough)

- $> 1 \log_{10}$ IU/mL increase in HCV RNA from nadir while on treatment, confirmed with 2 consecutive values (note, second confirmation value can be posttreatment), or last available on-treatment measurement with no subsequent follow up values (ie, rebound)
 - HCV RNA persistently \geq LLOQ through 8 weeks of treatment (ie, nonresponse)
- Relapse
- HCV RNA \geq LLOQ during the posttreatment period having achieved HCV RNA $<$ LLOQ at end of treatment, confirmed with 2 consecutive values or last available posttreatment measurement
- Characterization of HCV drug resistance substitutions at baseline, during, and after therapy with LDV/SOF

6.2.2. Analysis Methods for Secondary Efficacy Endpoints

For analyses of HCV RNA $<$ LLOQ by visit while on treatment and during the posttreatment (SVR) follow-up period, subjects will be assigned a value at each visit based on the analysis visit windows specified in Section 3.7.2. Missing values will be imputed based on the categorical imputation rules described in Section 3.5.1. The 2-sided 95% exact confidence interval based on Clopper-Pearson method will be provided for the percentage of subjects with HCV RNA $<$ LLOQ at each visit. The overall category for “HCV RNA $<$ LLOQ” will be split into the following 2 subcategories: “ $<$ LLOQ TND” for subjects with target not detected and “ $<$ LLOQ detected” for subjects with $<$ LLOQ detected in tabular displays.

Graphs for the percentage of subjects with HCV RNA $<$ LLOQ over time during treatment will be displayed.

Summary statistics will be presented for absolute values and change from baseline in HCV RNA (\log_{10} IU/mL) by visit through EOT. Imputation rules described in Section 3.5.1 will be used to assign HCV RNA values for missing values at a visit that are bracketed by “ $<$ LLOQ TND” and/or “ $<$ LLOQ detected”. Otherwise, a missing = excluded analysis will be performed. Plots of the mean \pm SD and median (Q1, Q3) of absolute values and changes from baseline in HCV RNA through EOT will be presented.

For the SVR12 endpoint analysis, a summary table of the number and percentage of subjects with SVR12, virologic failure (VF), and Other will be created. All subjects who achieve SVR12 will be categorized as SVR12. Virologic failure will be descriptively summarized as “on-treatment virologic failure” and relapse (which will be broken down by study drug completed yes/no). Subjects who do not achieve SVR12 and do not meet criteria for VF will be categorized as Other. The denominator for relapse will be the number of subjects who had HCV RNA $<$ LLOQ on their last observed on-treatment HCV RNA measurement; otherwise, the denominator will be the number of subjects in the FAS.

In addition, a summary table of the number and percentage of subjects with HCV RNA $<$ LLOQ and \geq LLOQ at the posttreatment follow-up visit (observed and imputed, with

reasons for imputed) will be provided for each posttreatment follow-up visit. 95% Clopper-Pearson exact CIs may be presented for the overall proportion of subjects with HCV RNA < LLOQ.

A concordance table between SVR12 and SVR24 will be provided. Subjects with both observed SVR12 and observed SVR24 data will be included for this analysis.

Drug resistant substitutions will be analyzed as part of the Virology Study Report.

6.3. Exploratory Endpoints of Interest

6.3.1. Definition of Exploratory Endpoints

PPD

- | [Redacted]
- | [Redacted]
- | [Redacted]
- | [Redacted]
- | [Redacted]
- | [Redacted]
- | [Redacted]
- | [Redacted]

6.3.2. Analysis Methods for Other Endpoints of Interest

PPD

[Redacted]

[Redacted]

PPD

A large rectangular area of the page is redacted with a solid blue color. The redaction covers the majority of the upper half of the page, starting below the header and ending above the section 6.4. The word 'PPD' is visible at the top left of this redacted area.

6.4. Changes From Protocol-Specified Efficacy Analyses

There are no changes from protocol-specified efficacy analyses.

7. SAFETY ANALYSES

7.1. Adverse Events and Deaths

7.1.1. Adverse Event Dictionary

Clinical and laboratory adverse events (AEs) will be coded using the current version of MedDRA. System organ class (SOC), high-level group term (HLGT), high-level term (HLT), preferred term (PT), and lower-level term (LLT) will be provided in the AE dataset.

7.1.2. Adverse Event Severity

Adverse events are graded by the investigator as Grade 1, 2, 3, or 4 according to toxicity criteria specified in the protocol. The severity grade of events for which the investigator did not record severity will be categorized as “missing” for tabular summaries and data listings and the most severe will be considered (for sorting purpose only) in data presentation.

7.1.3. Relationship of Adverse Events to Study Drug

Related AEs are those for which the investigator selected “Related” on the AE eCRF to the question of “Related to Study Treatment”. Events for which the investigator did not record relationships to study drug will be considered related to study drug for summary purposes. However, by-subject data listings will show the relationship as missing from that captured on the CRF.

7.1.4. Serious Adverse Events

Serious adverse events (SAEs) will be identified and captured as SAEs if AEs met the definitions of SAE specified in the study protocol. Serious adverse events captured and stored in the clinical database will be reconciled with the SAE database from the Gilead Drug Safety and Public Health Department before database finalization.

7.1.5. Treatment-Emergent Adverse Events

7.1.5.1. Definition of Treatment Emergent

Treatment-emergent adverse events (TEAEs) are defined as one or both of the following:

- Any AEs with an onset date on or after the study drug start date and no later than 30 days after permanent discontinuation of study drug.
- Any AEs leading to premature discontinuation of study drug.

7.1.5.2. Incomplete Dates

If the onset date of the AE is incomplete, then the month and year (or year alone if month is not recorded) of onset determine whether an AE is treatment emergent, as long as the AE

stop date is not prior to the first dose date of study drug. The event is considered treatment emergent if both of the following 2 criteria are met:

- The AE onset and end dates are the same as or after the month and year (or year) of the first dose date of study drug
- The AE onset date is the same as or before the month and year (or year) of the 30th day after the date of the last dose of study drug

An AE with completely missing onset and stop dates, or with the onset date missing and a stop date later than the first dose date of study drug, will be considered to be treatment emergent.

7.1.6. Summaries of Adverse Events and Deaths

A brief high-level summary of TEAEs will be provided by the number and percentage of subjects who had the following: any AE; any AE of Grade 3 or above; any AE of Grade 2 or above; any treatment-related AE; any treatment-related AE of Grade 3 or above; any treatment-related AE of Grade 2 or above; any SAE; any treatment-related SAE; any AE that led to premature discontinuation of LDV/SOF (90mg/400mg) or LDV/SOF(22.5mg/100mg); any AE leading to interruption of LDV/SOF (90mg/400mg) or LDV/SOF(22.5mg/100mg). All deaths (including those that are treatment emergent and those that are not treatment emergent) observed during the study will also be summarized and included in this table.

Adverse event summaries will provide the number and percentage of subjects with TEAEs by SOC and PT, based on the Safety Analysis Set as follows:

- All AEs
- AEs of Grade 3 or above
- AEs of Grade 2 or above
- All treatment-related AEs
- Treatment-related AEs of Grade 3 or above
- Treatment-related AEs of Grade 2 or above
- All SAEs
- All treatment-related SAEs
- All AEs leading to premature discontinuation of LDV/SOF
- Deaths

Multiple events will be counted only once per subject in each summary. Adverse events will be summarized and listed first in alphabetic order of SOC and then by PT in order of descending incidence of the pooled treatment groups within each SOC. In summaries by severity grade, the most severe grade will be used for those AEs that occurred more than once in an individual subject during the study.

In addition to the above summary tables, TEAEs will be summarized by PT only, in order of descending incidence for:

- AEs of Grade 3 or above
- All treatment-related AEs
- All SAEs
- AEs leading to premature discontinuation of LDV/SOF

In addition to the by-treatment summaries described above, data listings will be provided for the following:

- All AEs (with a variable indicating whether the event is treatment emergent)
- AEs of Grade 3 or above
- SAEs
- Deaths
- AEs leading to premature discontinuation of LDV/SOF

7.2. Laboratory Evaluations

Laboratory data collected during the study will be analyzed and summarized using both quantitative and qualitative methods. Summaries of laboratory data will be provided for the Safety Analysis Set and will include data collected up to the last dose of study drug plus 30 days for subjects who have permanently discontinued study drug or all available data at the time of the database snapshot for subjects those who were ongoing at the time of an interim analysis. The analysis will be based on values reported in conventional units. When values are below the limit of quantitation, they will be listed as such, and the closest imputed value will be used for the purpose of calculating summary statistics. For example, if “< 0.2” was recorded, a value of 0.1 will be used for the purpose of calculating summary statistics; if “< 0.1” was recorded, a value of 0.09 will be used for the purpose of calculating summary statistics. Hemolyzed test results will not be included in the analysis, but they will be listed in by-subject laboratory listings.

A by-subject listing for laboratory test results will be provided by subject ID number and visit in chronological order for hematology, serum chemistry, and urinalysis separately. Values falling outside of the relevant reference range and/or having a severity grade of 1 or

higher on the Gilead Grading Scale for Severity of Adverse Events and Laboratory Abnormalities will be flagged in the data listings, as appropriate.

No inferential statistics will be generated.

7.2.1. Summaries of Numeric Laboratory Results

Descriptive statistics (n, mean, SD, median, Q1, Q3, minimum, and maximum) will be provided for ALT, aspartate aminotransferase (AST), total bilirubin, alkaline phosphatase, hemoglobin, reticulocytes, white blood cell (WBC), neutrophils, lymphocytes, platelets, activated partial thromboplastin time (APTT), International Normalized Ratio of prothrombin time (INR), creatinine and CrCL (Schwartz formula) as follows:

- Baseline values
- Values at each postbaseline time visit
- Change from baseline at each postbaseline visit

A baseline laboratory value will be defined as the final assessment performed on or prior to the date/time of first dose of study drug. Change from baseline to a postbaseline visit will be defined as the visit value minus the baseline value. The mean, median, Q1, Q3, minimum, and maximum will be displayed to the reported number of digits; SD to the reported number of digits plus 1.

Median (Q1, Q3) of the observed values for ALT, AST, total bilirubin, alkaline phosphatase, creatinine, hemoglobin, reticulocytes, WBC, neutrophils, lymphocytes, and platelets will be plotted using a line plot by visit.

In the case of multiple values in an analysis window, data will be selected for analysis as described in Section 3.8.3 (Selection of Data in the Event of Multiple Records in a Window).

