4.3. Exclusion Criteria

Subjects who meet *any* of the following exclusion criteria are not to be enrolled in this study.

- 1) Co-infection with HIV, acute hepatitis A virus (HAV) infection or chronic HBV coinfection (HBsAg positive [HBsAg+] at screening)
- 2) Decompensated liver disease defined as INR > 1.2 x ULN, platelets < 50,000/mm³, serum albumin < 3.0 g/dL, or prior history of clinical hepatic decompensation (eg, ascites, jaundice, encephalopathy, variceal hemorrhage)
- 3) Evidence of a gastrointestinal malabsorption syndrome that may interfere with absorption of orally administered medications
- 4) Chronic liver disease of non-HCV etiology (eg, hemochromatosis, Wilson's disease, alpha-1 antitrypsin deficiency)
- 5) Evidence of hepatocellular carcinoma (HCC) or other non-hematologic malignancy (with the exception of certain resolved skin cancers)

Note: liver imaging within 6 months of baseline/Day 1 is required in patients with cirrhosis to exclude HCC

- 6) History of solid organ or bone marrow transplantation
- 7) Active or recent history (\leq 1 year) of alcohol or drug abuse
- 8) Serum creatinine > 1.5 mg/dL
- 9) Estimated glomerular filtration rate < 90 mL/min/1.73m², as calculated by the Schwartz formula
- 10) Investigational agents taken within the past 28 days (except with the prior written approval of the Sponsor)
- 11) Use of any prohibited concomitant medications as described in Section 5.3
- 12) Pregnant or lactating subjects
- 13) Sexually-active males or females of childbearing potential who are not willing to use an effective method of contraception during the study (see [Appendix 4](#) for further details)
- 14) Unable to swallow the LDV/SOF FDC 90mg/400mg and the LDV/SOF FDC 22.5mg/100mg placebo tablets
- 15) Known hypersensitivity to LDV, SOF, metabolites, or formulation excipients
- 16) Subject unable to comply with the dosing instructions for study drug administration and/or unable to complete the study schedule of assessments

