6.7. Procedures and Specifications

6.7.1. Clinical Laboratory Analytes

- Hematology: Hematocrit, hemoglobin (Hb), platelet count, red blood cell count (RBC), white blood cell count (WBC) with differential (absolute and percentage) including lymphocytes, monocytes, neutrophils, eosinophils, basophils, reticulocyte count and MCV.
- Coagulation: INR, prothrombin time (PT), activated partial thromboplastin time (APTT).
- Chemistry: Alanine aminotransferase (ALT/SGPT), aspartate aminotransferase (AST/SGOT), albumin, alkaline phosphatase, creatinine, total bilirubin (reflex to direct bilirubin), glucose (non-fasting), potassium, sodium; gamma-glutamyl transferase (GGT)
- Fibrotest
- APRI
- Virological Tests: Serologies for HCV, HBV (HBsAg, HBsAb, HBcAb), HAV, and HIV. HCV RNA will be measured using the COBAS® AmpliPrep/COBAS® TaqMan® HCV Quantitative Test, version 2.0. HCV genotype and subtype will be determined using the Siemens VERSANT® HCV Genotype INNO-LiPA 2.0 Assay. HBV DNA testing will be performed only in subjects HBcAb positive at Screening. Alternate assays may be used if the above assays are not available or are not definitive.

- IL28B genotype will be determined by polymerase chain reaction (PCR) amplification of the SNP, rs12979860. Alternate assays may be used if this assay is not available.
- Pregnancy Tests: Serum β -hCG or urine β -hCG (if positive, requires immediate confirmation with serum β -hCG).

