ENZYMES				
	Grade 1	Grade 2	Grade 3	Grade 4
AST (SGOT)	1.25 to 2.50 × ULN	> 2.50 to 5.00 × ULN	> 5.00 to 10.00 × ULN	> 10.00 × ULN
ALT (SGPT)	1.25 to 2.50 × ULN	> 2.50 to 5.00 × ULN	> 5.00 to 10.00 × ULN	> 10.00 × ULN
GGT	1.25 to 2.50 × ULN	> 2.50 to 5.00 × ULN	> 5.00 to 10.00 × ULN	> 10.00 × ULN
Alkaline Phosphatase	1.25 to 2.50 × ULN	> 2.50 to 5.00 × ULN	> 5.00 to 10.00 × ULN	> 10.00 × ULN
Total Amylase	> 1.0 to 1.5 × ULN	> 1.5 to 2.0 × ULN	> 2.0 to 5.0 × ULN	> 5.0 × ULN
Pancreatic Amylase	> 1.0 to 1.5 × ULN	> 1.5 to 2.0 × ULN	> 2.0 to 5.0 × ULN	> 5.0 × ULN
Lipase	> 1.0 to 1.5 × ULN	> 1.5 to 3.0 × ULN	> 3.0 to 5.0 × ULN	> 5.0 × ULN
Albumin Pediatrics <16 years	-	2.0 to < LLN g/dL 20 to < LLN g/L	< 2.0 g/dL < 20 g/L	NA
≥ 16 years	3.0 g/dL to < LLN 30 g/L to < LLN	2.0 to < 3.0 g/dL 20 to < 30 g/L	< 2.0 g/dL < 20 g/L	NA

URINALYSIS				
	Grade 1	Grade 2	Grade 3	Grade 4
Hematuria (Dipstick)	1+	2+	3-4+	NA
Hematuria (Quantitative) See Note below				
Females	>ULN - 10 RBC/HPF	> 10-75 RBC/HPF	> 75 RBC/HPF	NA
Males	6-10 RBC/HPF	> 10-75 RBC/HPF	> 75 RBC/HPF	NA
Proteinuria (Dipstick)	1+	2-3+	4+	NA
Proteinuria, 24 Hour Collection				
Adult and Pediatric ≥ 10 Years	200 to 999 mg/24 h	>999 to 1999 mg/24 h	>1999 to 3500 mg/24 h	> 3500 mg/24 h
Pediatric > 3 Mo to < 10 Years	201 to 499 mg/m ² /24 h	>499 to 799 mg/m ² /24 h	>799 to 1000 mg/m ² /24 h	> 1000 mg/ m ² /24 h
Glycosuria (Dipstick)	1+	2-3+	4+	NA

Notes:

- Toxicity grades for Quantitative and Dipstick Hematuria will be assigned by Covance Laboratory, however for other laboratories, toxicity grades will only be assigned to Dipstick Hematuria.
- With the exception of lipid tests, any graded laboratory test with a result that is between the LLN and ULN should be assigned Grade 0.
- If the severity of a clinical AE could fall under either one of two grades (e.g., the severity of an AE could be either Grade 2 or Grade 3), select the higher of the two grades for the AE.

CARDIOVASCULAR				
	Grade 1	Grade 2	Grade 3	Grade 4
Cardiac Arrhythmia (general) (By ECG or physical exam)	Asymptomatic AND No intervention indicated	Asymptomatic AND Non-urgent medical intervention indicated	Symptomatic, non-life-threatening AND Non-urgent medical intervention indicated	Life-threatening arrhythmia OR Urgent intervention indicated
Cardiac-ischemia/Infarction	NA	NA	Symptomatic ischemia (stable angina) OR Testing consistent with ischemia	Unstable angina OR Acute myocardial infarction

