7.2.3.1. Treatment-Emergent Laboratory Abnormalities

Treatment-emergent laboratory abnormalities are defined as values that increase at least 1 toxicity grade from baseline at any postbaseline time point, up to and including the date of last dose of study drug plus 30 days for subjects who permanently discontinued study drug, or all available data in the database snapshot for subjects who were still on treatment at the time of an interim analysis. If the relevant baseline laboratory value is missing, then any abnormality of at least Grade 1 will be considered treatment emergent.

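### Below age 16, albumin that starts between 3.0 g/dL and the LLN can fall to 2.0-2.9 g/dL and enter no laboratory table

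*SAP*

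**What the plan says.** Protocol 6.7.1 places albumin in the chemistry panel ("aspartate aminotransferase (AST/SGOT), albumin, alkaline phosphatase, creatinine"). By the schedule in Protocol Appendix 2, chemistry is drawn at screening, Day 1, Weeks 4, 8 and 12, early discontinuation and Post-Treatment Week 4. It is not drawn at Week 1.

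Exclusion criterion 2 in Protocol 4.3 defines decompensated liver disease by three laboratory markers (INR, platelets and albumin) or by clinical history. The albumin part reads "serum albumin < 3.0 g/dL".

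Protocol Appendix 3 grades albumin differently by age. In the row "Albumin Pediatrics <16 years" the Grade 1 cell is empty, Grade 2 is "2.0 to < LLN g/dL 20 to < LLN g/L", and Grade 3 is anything below 2.0 g/dL. From 16 years, Grade 1 is "3.0 g/dL to < LLN 30 g/L to < LLN", Grade 2 is 2.0 to below 3.0 g/dL, and Grade 3 is again below 2.0 g/dL. A result inside the normal range is Grade 0.

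SAP 7.2.3.1 defines treatment-emergent laboratory abnormalities as "values that increase at least 1 toxicity grade from baseline". If the baseline is missing, any graded abnormality counts. The graded tables and the Grade 3 listing in SAP 7.2.3.2 are limited to treatment-emergent abnormalities.

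SAP 7.2.1 names the analytes that get by-visit values and change from baseline. The list includes INR and platelets ("reticulocytes, white blood cell (WBC), neutrophils, lymphocytes, platelets, activated partial thromboplastin time (APTT), International Normalized Ratio of prothrombin time (INR), creatinine and CrCL") and the liver enzymes and bilirubin, but not albumin.

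**The concern.** Each of these rules is ordinary by itself; the gap comes from combining them. Below 16, a single grade covers both a value just under normal and a value well under 3.0 g/dL. The tables count only a change of grade, and there is no numeric summary to show movement within one. Whether a given fall is tabulated therefore depends on the subject's age and not on the size of the fall.

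Safety and tolerability form one of the primary objectives. Of the three laboratory markers in exclusion 2, albumin is the only one without a numeric summary, and below 16 it has the coarser grading. With 19 subjects enrolled (SAP 1.3), one uncounted subject is 1/19 = 5.3% of the trial.

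**Working it through.** The documents state no figure on this point to reproduce, so the check applies the grading and counting rules to hypothetical values.

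**Inputs.** Grade bands: Protocol Appendix 3. Counting rule: grade after baseline minus grade at baseline is at least 1 (SAP 7.2.3.1). Lowest albumin allowed by exclusion 2: 3.0 g/dL. Albumin LLN: not given. It is assumed to exceed 3.0 g/dL, because the Grade 1 band from age 16 runs from 3.0 g/dL up to the LLN and would otherwise be empty. Values of 3.2, 3.5 and 3.8 g/dL were tried, with the same LLN at both ages.

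**Examples with LLN 3.5 g/dL.**

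| Fall (g/dL) | Age 14 | Age 16 |
|---|---|---|
| 3.2 to 2.8 | Grade 2 to 2, not counted | Grade 1 to 2, counted |
| 3.4 to 2.0 | Grade 2 to 2, not counted | Grade 1 to 2, counted |
| 3.2 to 1.9 | Grade 2 to 3, counted | Grade 1 to 3, counted |
| 4.0 to 3.3 | Grade 0 to 2, counted | Grade 0 to 1, counted |
| 4.0 to 2.8 | Grade 0 to 2, counted | Grade 0 to 2, counted |

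The last two rows show a second, weaker effect. From a normal baseline the fall is counted, but below 16 both falls appear as Grade 2, so the table does not show which one passed 3.0 g/dL.

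**Enumeration.** Take every baseline from 3.0 to 5.0 g/dL and every later value from 2.0 to 2.9 g/dL, in steps of 0.1. The number of cases with baseline below the LLN is (LLN - 3.0)/0.1 baselines times 10 later values.

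| Assumed LLN | Baseline 3.0 to < LLN: cases | Not counted, under 16 | Not counted, 16 or over | Baseline at or above LLN: cases | Not counted, either age |
|---|---|---|---|---|---|
| 3.2 | 2 x 10 = 20 | 20 | 0 | 190 | 0 |
| 3.5 | 5 x 10 = 50 | 50 | 0 | 160 | 0 |
| 3.8 | 8 x 10 = 80 | 80 | 0 | 130 | 0 |

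These are grid points, not subjects or probabilities. They show that the rule is all or nothing within the affected baseline band.

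**Largest fall inside one grade, under 16.** From one step below the LLN down to 2.0 g/dL: (3.1 - 2.0)/3.1 = 35.5%, (3.4 - 2.0)/3.4 = 41.2% and (3.7 - 2.0)/3.7 = 45.9% at LLN 3.2, 3.5 and 3.8.

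**Other displays.** The by-subject chemistry listing (SAP 7.2) shows every result and flags those out of range or graded. Protocol 7.1.3 keeps laboratory findings of no clinical significance out of the adverse event record. It requires an event when the finding needs intervention, changes study drug dosing, or comes with symptoms and meets the event definition. The adverse event tables therefore catch some of these falls but not all.

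**The case against.** The strongest reply is that the gap is small and the plan breaks no promise. Protocol 8.6.3 commits only to numeric summaries of selected laboratory data, and the selection already covers ALT, AST, bilirubin, alkaline phosphatase, INR, platelets and, in SAP 7.2.2, APRI. The 3.0 g/dL figure is an entry criterion. The laboratory stopping rules in Protocol 7.5.1 set no albumin threshold. A fall that matters clinically should become an adverse event, and with 19 subjects the flagged listing can be read line by line.

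Most of this stands. It makes the point a reporting gap, not a conflict between documents, and it limits the consequence. It does not explain why the same fall is tabulated at 16 and not at 14, or why one of the three exclusion 2 markers was left out. Using 3.0 g/dL as a descriptive mark is not arbitrary either: the grading scale itself divides Grade 1 from Grade 2 there from age 16.

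Three stronger readings are tempting, and the documents do not support them.

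- A reader might infer that no fall through 3.0 g/dL below age 16 reaches a table. From a normal or missing baseline it is counted as treatment-emergent Grade 2, and a fall below 2.0 g/dL is Grade 3 and is tabulated.
- A reader might treat every subject aged 12 to 15 as affected. Only those who start between 3.0 g/dL and the LLN are, and the documents give neither their number nor the LLN.
- A reader might argue that exclusion 2 makes every post-baseline value below 3.0 g/dL a new crossing. Screening can precede Day 1 by 28 days, or 42 with approval (Protocol 6.1.1). The analysis baseline is the latest result up to first dose (SAP 7.2.1). A subject could pass at screening and have a baseline below 3.0 g/dL.

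**Conclusion.** The point holds within a defined condition: a subject under 16, baseline albumin at least 3.0 g/dL but below the LLN, a fall to 2.0-2.9 g/dL, and no adverse event recorded for it. Such a fall enters no table and is visible only as a flagged result in the by-subject listing. From a normal or missing baseline it is counted, but without showing whether 3.0 g/dL was passed.

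The result depends on the LLN being above 3.0 g/dL for subjects under 16; at 3.0 g/dL or lower the affected band disappears. Over the assumed LLN range the band is 0.2 to 0.8 g/dL wide. No number of subjects can be attached to it from the documents. The consequence is modest: no efficacy estimate changes and no data are lost. Since the tables serve a primary objective and the repair costs little, it is worth making.

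**What to change.** Add albumin to the analytes in SAP 7.2.1, with value and change from baseline at each visit that has chemistry. The minimum at each visit then shows a low value whatever its grade.

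Add one descriptive row in SAP 7.2.3.2: number and percentage of subjects with baseline albumin of at least 3.0 g/dL and any later value below 3.0 g/dL, up to last dose plus 30 days. The baseline condition keeps out subjects who were already below 3.0 g/dL at first dose. On the grid above, the row captures all 20, 50 and 80 missed cases.

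The grading scale, eligibility and stopping rules stay as they are; the row is for reporting only. The cost is one analyte in an existing table and one extra row, with no new data. If the SAP is already final, SAP section 1 provides for recording the change in the clinical study report.
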